In the usual care group, the proportion of patients who underwent IAC is a measure of adherence. In the experimental group, the proportion of patients who underwent IAC is of relevance as it reflects the limits of the non-invasive approach.

- The effect of intervention on changes over time of the SOFA score, the blood haemoglobin level, haematocrit, mean daily blood volume drawn for lab testing, mean daily amount of intravenous fluids given for rapid vascular volume expansion, mean daily fluid balance, daily maximum pain and associated 95%CI will be estimated using mixed linear models, after data transformation if necessary.
- Duration of mechanical ventilation will be analysed using a competing risk approach, with death as competing risk.
- The effect of intervention on proportion of patients treated by renal-replacement therapy or by vasopressor, proportions of patients with arterial and central venous catheter-related infections or bloodstream infections and associated 95%CI will be estimated using the competing risk approach, with death as competing risk.
- The effect of intervention on number of blood cultures performed, number of attempts at arterial puncture, number of red blood cell packs transfused, number of arterial and central venous catheter insertion and associated 95%CI will be estimated using negative binomial models with duration of ICU stays as offset variable.
- Two-sided 95% CIs of median differences of free-days (Ventilator-free days, renal replacement therapy-free days, vasopressor therapy-free days) will be estimated.
- Duration of ICU and hospital stay: 2-sided 95% CIs of median differences will be estimated.

- The effect of intervention on ICU and hospital mortality and 95% CI will be estimated using competing-risk model with ICU and hospital discharge alive as competing events with death during the stay.

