Deferring arterial catheterization in critically ill patients with shock – EVERDAC trial

STATISTICAL ANALYSIS PLAN — December 2024

The initial Statistical Analysis Plan established before launching the study and published in BMJ Open in 2021 ([name] et al. BMJ Open 2021;11:e044719. doi:10.1136/bmjopen-2020-044719) was amended after the blind review of the data in December 2024.

Level of statistical significance

Statistical significance threshold will be set at 5%, and 95% two-sided confidence intervals (95%CI) will be calculated for all estimates.

Analyzed population

All randomized patients, except for patients who secondarily object to the use of their data or protected under guardianship, will be included in the analysis. No interim analysis will be performed.

Two per-protocol populations were defined during the blind review:

- In the first per-protocol population, we will exclude patients wrongly included, and patients from the noninvasive group in whom the arterial catheter previously inserted was not removed after the randomization. In the invasive group, we will exclude the patients who either did not undergo an attempt at arterial catheter insertion or had the arterial catheter insertion more than 24h after randomization.
- In the second per-protocol population, we will exclude patients from the invasive group who did not receive an arterial catheter within 24h after randomization, regardless of the reason (unsuccessful arterial catheter insertion, no attempt of arterial catheter insertion or insertion occurring more than 24h after randomization). The per-protocol population in the noninvasive group will remain unchanged for the second per-protocol analysis.

Description of baseline characteristics

All data recorded at baseline will be summarized by treatment group using means and standard deviation for normally distributed quantitative variables, median and interquartile range for other quantitative variables, and counts and percentages for qualitative variables. No statistical test will be used.

Primary outcome

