The primary analysis of the primary outcome will be the determination of the between-group difference (noninvasive group minus invasive group) in rates of day-28 mortality, estimated with a binomial generalized estimating equation (GEE) model with identity link adjusted on the stratification variables and on the center effect (Pedroza 10.1186/s12874-016-0217-0). A switch from noninferiority to superiority is *a priori* planned if the hypothesis of noninferiority with a noninferiority margin of 5 percentage points is verified. These hypotheses will be assessed using the stratified Farrington-Manning test for differences in proportions.

Secondary outcomes analysis

Statistical analyses for secondary outcomes will not be adjusted for multiplicity; therefore, secondary-outcome findings should be interpreted as exploratory.

- Day-90 mortality will be analyzed with the same model as the primary outcome .
- Cumulative incidence of death from randomization through Day 90 will be analyzed with a Cox model.
- ICU mortality and hospital mortality will be analyzed in a competing risks framework. A hazard ratio will be computed from the whole groups using a Fine and Gray regression model. ICU discharge or hospital discharge will be considered as competing events.

The following outcomes will be described with median and quartiles and compared between groups using median differences:

- Duration of ICU stay from randomization to discharge.
- Duration of hospital stay from randomization to discharge.
- Duration of mechanical ventilation from randomization and Day 28.
- Ventilator-free days from randomization to Day 28.
- Renal replacement therapy-free days from randomization to Day 28.
- Vasopressor therapy-free days from randomization to Day 28.

For each outcome, 95% confidence intervals of the median difference will be computed using unstratified bootstrapping (10,000 samples with replacement). Vasopressor therapy-free days, renal replacement therapy-free days and duration of mechanical ventilation do not account for the competing risk of death.

The following outcomes will be represented with boxplots at each day:

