Patient-reported pain and discomfort related to the device used for BP monitoring will be measured daily using 4 scales rating from 0 to 10. Each day, a patient will be considered as experiencing pain and/or discomfort if at least one scale is ≥ 4 (Gerbershagen, DOI: 10.1093/bja/aer195). The proportions of patients experiencing at least one day with pain and/or discomfort will be compared with a chi-squared test. The numbers of days with pain and/or discomfort will be compared between the groups with the use of a quasi-Poisson regression model and expressed as rate ratios, with the duration of stay in the ICU as the offset.

- The number of patients reaching the predefined upper limit of vasopressor dosage ($>2.5\mu\text{g}/\text{kg}/\text{min}$ of norepinephrine tartrate plus epinephrine) will be estimated in each group, and day 28 mortality will be described amongst these severely ill patients.

Subgroup analyses

No subgroup analyses were prespecified.

Implementation

Statistician: [name] , Centre d'Investigation Clinique INSERM 1415, CHRU de Tours.

Software: R version 4.3.1

SUMMARY OF CHANGES FROM THE INITIAL PROTOCOL AND JUSTIFICATIONS

Changes in the analyses of the primary outcome

Additional methodological recommendations were identified on current recommendations to estimate a difference in proportions (Pedroza 10.1186/s12874-016-0217-0), recommendations on adjusting stratification variables (Sullivan 10.1002/sim.10060) and recommendations on taking account of the center effect for multicenter studies (Kahan 2013 10.1002/sim.5667, Pedroza 10.1186/s12874-016-0217-0). The final GEE model was established during the analysis of the data, as we observed a significant within-center correlation (Intra-class correlation coefficient = 0.02 for day 28 mortality in each group).

To quantify how strongly our data reject the possibility that the true difference exceeds the 5% noninferiority margin, we employed a stratified Farrington–Manning test. This approach formally tests the noninferiority hypothesis and complements the estimation of the between-group difference obtained with the GEE model. This decision was made during the analysis of the data.

Changes in the analyses of the secondary outcomes

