Patient-reported pain and discomfort related to the device used for BP monitoring was initially planned to be analyzed as a quantitative outcome but was binarized because of the over-representation of 0 in responses (>78.4%) for each scale and each visit (0 being equivalent to no pain). This analysis was chosen during the analysis of the data.

Contrary to what was written in the initial statistical analysis plan, the analysis of vasopressor therapy-free days, renal replacement therapy-free days and duration of mechanical mechanical ventilation do not account for competing risk of death or ICU discharge. This change was made before the blind review.

Additional safety analysis

Upon reviewing the data, we observed that the number of patients in the noninvasive group who underwent arterial catheterization after reaching the vasopressor dose of 2.5 µg/kg/min—a predefined safety criterion for catheterization—was higher than anticipated. This led us to question whether the high vasopressor dose might have resulted from the intervention, specifically due to potential inaccuracies in blood pressure measurements with oscillometric brachial cuff devices. Consequently, we planned to also report the number of patients in the control group (invasive group) who reached this vasopressor threshold and document the difference between groups.

Missing analyses and secondary outcomes

The following secondary outcomes were initially planned in the original protocol but cannot be analyzed due to lack of access to reliable data.

- Numbers of local infections of arterial and central venous during ICU stay (number of new cases per 1000 catheter-days).
- Numbers of arterial and central venous catheter-related infections during ICU stay, expressed as the incidence of new cases per 1000 ICU-days, including local and catheter-related bloodstream infections as consensually defined.
- Number of bloodstream infections during ICU stay, catheter-related or not.
- Number of peripheral venous punctures for laboratory tests.

The protocol published in BMJ open stated that a sensitivity analysis would be adjusted on the location of the arterial catheter. This analysis was removed before the blind review.

Further clarifications

For median differences, confidence intervals are computed using unstratified bootstrapping (10,000 samples with replacement). This precision was added before the blind review.

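### Pain and discomfort: the planned full-scale analysis was replaced, while the data were being analysed, by two comparisons at a cut-off of 4, and no full-scale analysis is kept

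*SAP*

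**What the plan says.** **Protocol.** Section 2.3 lists patient-reported pain and discomfort from the blood-pressure device as a secondary outcome, rated once a day when the patient is awake and able to judge it. Appendix 1 gives four 0-10 ratings: discomfort, pain at the site, pain spreading over the limb, and numbness. Section 6.2 plans, in its list of outcomes followed over time, that "daily maximum pain and associated 95%CI will be estimated using mixed linear models, after data transformation if necessary". Under General principles, the same section allows later changes to the analysis plan only before unblinding.

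**SAP.** Under Safety outcomes and analyses, a day counts as positive if any of the four ratings is 4 or more; an outside source is cited for the cut-off. Two comparisons follow. First: "The proportions of patients experiencing at least one day with pain and/or discomfort will be compared with a chi-squared test". Second: "The numbers of days with pain and/or discomfort will be compared between the groups with the use of a quasi-Poisson regression model", "expressed as rate ratios, with the duration of stay in the ICU as the offset". Neither is named as the main one. The general rule is "Statistical significance threshold will be set at 5%, and 95% two-sided confidence intervals (95%CI) will be calculated for all estimates". Under Secondary outcomes analysis: "Statistical analyses for secondary outcomes will not be adjusted for multiplicity", and those findings are to be read as exploratory. The summary of changes says the quantitative analysis was given up because more than 78.4% of responses were 0 for each scale and visit, and adds: "This analysis was chosen during the analysis of the data".

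**The concern.** Device-related pain and discomfort is a direct patient-reported contrast between a cuff and a catheter, in an open-label trial. The comparison the reader will see rests on a rule (four ratings, any one of them, cut at 4) that was not in the protocol and was fixed after analysis had begun. With no full-scale result beside it, nobody can tell whether the conclusion depends on that rule.

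There is a second weakness. Only awake, capable patients give ratings, but the rate comparison divides by all ICU days, so unrated days count as pain-free. A difference between arms in the share of ICU days that were rated could then look like a difference in pain.

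**Working it through.** **Timing.** Protocol 6.2 requires changes before unblinding. The SAP's summary of changes dates several other changes before the blind review, but places this one in the data analysis. It does not say whether allocation was visible when the choice was made. At that stage an intra-class correlation for day-28 mortality had been computed in each group, so arms were separated for at least one outcome. That does not show that pain was seen by arm.

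**Does the reason support the rule?** The stated figure is more than 78.4% zeros per scale and visit, so fewer than 100 − 78.4 = 21.6% of ratings are 1 or more.
- A surplus of zeros separates 0 from 1 and above. It could motivate a zero/non-zero split, an ordinal model or a zero-inflated model. It does not separate 3 from 4.
- The figure is for single scales. If the planned maximum runs over all four, its non-zero share is below 4 × 21.6 = 86.4%, so its share of zeros is only known to exceed 100 − 86.4 = 13.6%. The SAP does not give the share of zeros for the maximum itself.

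**Which variable?** Protocol 6.2 says only daily maximum pain and does not list the scales that enter it. If all four enter, the SAP's daily rule is that maximum cut at 4. If only the pain ratings enter, adding discomfort and numbness is a further change.

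**Exposure.** Let λ be the rate of positive days per rated day and f the share of ICU days rated. The rate per ICU day is f × λ, so the SAP's rate ratio estimates (f₁/f₀) × (λ₁/λ₀). An equal f cancels; an unequal f biases the ratio by the factor f₁/f₀. The documents do not report f. The any-day proportion also rises with the number of rated days.

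**Two tests at 5%, for scale only.** The documents give no error rate, effect size, spread or number of rated patients for pain, so there is no planned figure to reproduce.
- If independent: 1 − 0.95² = 9.75%.
- As correlated normal statistics: 9.1% at correlation 0.5 and 7.8% at 0.8.
- The two tests use the same positive days, so they are correlated. A null simulation used these assumptions: 200, 350 or 500 rated patients per arm; 80% or 90% zeros per scale; between-patient SD 0.5, 1 or 2; median ICU stay 7 days, capped at 28; half of ICU days rated; 4,000 runs per setting. With each test calibrated to 5%, at least one was positive in 7.6% to 8.5% of runs: 7.6/5 = 1.5 to 8.5/5 = 1.7 times the nominal level.
- Uncalibrated, with ICU stay as the offset, the range was 8.3% to 11.8%. The excess arises because the quasi-Poisson test alone rejected 5.6% to 9.3% of the time in that assumed model, not because two tests were run.

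**The case against.** The strongest reply is that the SAP already deals with most of this. Pain is a secondary outcome in protocol 2.3, and the SAP reports its change under the secondary outcomes, so the exploratory and unadjusted status reasonably applies even though the tests sit under a safety heading. Being affected at all and the burden of affected days are distinct descriptions. The timing is disclosed, the cut-off is referenced, the stated reason mentions no between-group result, and a linear model on scores with this many zeros would itself be questionable.

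Most of that stands. It also disposes of three stronger readings that a reader might infer:
- **That the false-positive rate doubles.** No 5% family-wise rate is promised for pain, and doubling is close to the independence bound, which does not suit two tests built on the same days.
- **That the cut-off was searched for.** One cited cut-off appears, and nothing in the documents shows that others were tried.
- **That power is lost.** Without an effect size, a spread or a number of rated patients this cannot be derived. The direction depends on the effect: a shift of the whole score tends to favour a full-scale analysis, while a change only in intensity among those with pain can favour the cut-off.

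The reply does not cover the absence of any full-scale analysis, the merging of 1 to 3 with 0 without a reason, or the exposure used for the rate.

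**Conclusion.** The point holds as one about a late, data-driven change of analysis with no planned counterpart kept beside it. It is not a breach of error control. The documents leave open whether the choice was made blind to allocation, so the protocol's timing rule raises a fair question rather than a proven violation. The figure of about 8% (roughly 1.5 to 1.7 times 5%) shows scale only and rests on the assumed simulation inputs. The exposure problem matters only if the share of rated ICU days differs between arms, which the documents do not report. The primary outcome is unaffected.

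**What to change.** In the SAP, under Safety outcomes and analyses:

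1. Make the daily maximum score (0-10) over rated days the reference pain comparison, using a method that tolerates the zeros, for example a proportional-odds mixed model, with an estimate and 95% CI. State which of the four scales enter the maximum.
2. Keep the any-day and rate-of-days analyses at 4 or more as supportive, labelled post hoc and chosen during the data analysis.
3. Use rated days, not ICU stay, as the exposure for the rate, and report the number of rated days by arm.
4. State that the exploratory, unadjusted status of secondary outcomes covers the pain comparisons.

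The cost is SAP wording and one extra model on data already collected. An odds ratio is less intuitive than a proportion, which can still be shown. The ordinal form would itself be chosen after the zeros were seen, and the report should say so. Using rated days removes the assumption that unrated days are pain-free; it does not remove the selection of patients well enough to give ratings.

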- Number of Adverse Events of special interest (Ischemia and/or necrosis of finger(s) or toe(s), documented bowel ischemia, occurrence or worsening of acute renal failure with need of renal replacement therapy, need of tracheal intubation in a patient previously not intubated, Cardiac arrest, nerve injury of upper limb(s), skin lesions at cuff location or at IAC insertion site, arterial thrombosis, hematoma, arterial pseudo aneurysm, haemorrhage at IAC insertion site either during IAC placement or later)
- Incremental Cost-Effectiveness Ratio (ICER): «Cost/Life day gained at 28 days», from the health system viewpoint, between the non invasive strategy and the recommended invasive strategy: $(\text{Costs}_{\text{NIBP}} - \text{Costs}_{\text{IAC}}) / (\text{Life expectancy at D28}_{\text{NIBP}} - \text{Life expectancy at D28}_{\text{IAC}})$
- Budget impact analysis of the generalization of the non-invasive strategy (in case of demonstrated non inferiority) in France from the viewpoint of the French health system on a 5 years' time frame
- Patient-reported pain and discomfort related to the device used for BP monitoring will be assessed using numerical scales in both groups, once a day as soon as the patients are awakened and capable of correctly evaluating their pain and discomfort (cf. APPENDIX 1)

3. Interventions

Once included, the patient will be randomly assigned, for the 28 following days, to one of the following strategies:

a) **“usual care”**: An IAC will be inserted as soon as possible (within the first four hours after randomization)

and will be maintained except in case of IAC futility (as defined below), suspected or proven IAC related infection or thrombosis (at discretion of attending physician) until day 28 or ICU discharge (whichever comes first). After day 28, clinicians may choose to maintain or to remove IAC.

During the intervention period, in case of removal for accidental or other reasons than futility (i.e. IAC infection, IAC dysfunction, unavailability to draw blood), another IAC should be inserted during the next four hours (insertion site at the discretion of the attending physician).

In case of IAC removal for other futility criteria than decision of palliative care, an IAC will be inserted within the four hours of new onset of circulatory failure as defined below:

- Presence of
 - Persisting hypotension (systolic blood pressure less than 90 mmHg or mean arterial blood pressure less than 65 mmHg) for more than 4 hours

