4.5. Study outline

4.6. Schedules of procedures for each enrolled patient

	Inclusion	Short-term follow up until D28 or discharge from ICU (whichever comes first)			Long-term follow up
Study Day 1 starts once patient is randomized		D1, D2, D3	D4, D5, D6, D7	D8 to D28	D90
Inclusion/exclusion criteria	X				
Informed consent	X				
Randomisation	X				
Delayed pursuit consent if applicable		X	X	X	X
Clinical assessment (heart rate, blood pressure, SpO ₂ , pain assessed during transcutaneous vascular puncture ^{a,e} , fluid balance ^b)		X	X	X	
Catheter evaluation (IAC insertion, IAC removal, catheter-related infection)		X	X	X	
Laboratory sampling status (blood volume draw, number of attempts at arterial puncture)		X	X	X	
Therapeutic assessment (number of packs of red blood cells transfused)		X	X	X	
Supportive therapy assessment (respiratory status, ventilator settings ^c , renal replacement therapy ^c , vasopressor support ^b)					
Census evaluation (survival status, in ICU, in Hospital)		X	X	X	X
Specific laboratory testing for the study (SOFA)		X	X		
Blood haemoglobin ^d		X	X	X	
Number of arterial and venous punctures for lab tests, arterial catheter insertion and set up of monitor, blood drawings from arterial catheter or other vascular line, through ICU stay ^e		X	X	X	
Microcosting of staff time and equipment used for arterial and venous punctures for lab tests, arterial catheter insertion and set up of monitor, blood drawings from arterial catheter or other vascular line, through ICU stay ^e		X			
Adverse events/Serious adverse events ^f		X	X	X	X
Query on the French National Hospital Discharge Database (at the end of the study)		X	X	X	

^a: assess by visual or numeric scale for patients able to communicate and by Behavioural Pain Scale(66) otherwise

^b: fluid balance will be assessed only from D1 to D7

^c: if applicable

^d: if available

^e: on a 10% random sample of study population

^f: Collection and reporting of adverse events will begin once the informed consent is signed

Patients' follow-up:

Patients will be examined for signs of shock and organ failures throughout their ICU stay, as done in routine practice.

Their deceased/alive status will be recorded at ICU discharge, hospital discharge, by day 28 and by day 90

Lost-to-follow-up

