
19. APPENDIX 1

In both groups, once the patient alert and capable, we will assess his/her pain and discomfort related to the BP measuring device in place.

Whatever the group the patient is assigned to, he/she will rate, once a day, his/her pain and discomfort using the following 11-point numerical scales.

- Does the presence of the BP measuring device (catheter or cuff) cause you some discomfort?
To be rated from 0 (no discomfort at all) to 10 (very important and permanent discomfort).
- Does the presence of the BP measuring device (catheter or cuff) cause you some pain, either continuous or intermittent, at the site of measurement (location of catheter or of cuff)?
To be rated from 0 (not painful at all) to 10 (highest pain ever experienced).
- Does the presence of the BP measuring device (catheter or cuff) cause you some pain, either continuous or intermittent, that extends beyond the site of measurement and spreads over the entire limb?
To be rated from 0 (not painful at all) to 10 (highest pain ever experienced).
- Does the presence of the BP measuring device (catheter or cuff) cause you some numbness in the hand (or in the foot; depending upon location of the BP measuring device)?
To be rated from 0 (no numbness at all) to 10 (highest numbness ever experienced).

20. APPENDIX 2

The following pages provide diagrams to help estimate true values of arterial blood gases (pH, PaCO_2 , SaO_2) and lactate, using central venous blood analysis, SpO_2 , and, only for pH, clinical characteristics.

Functions used to calculate these estimates were derived and validated in a large cohort of ICU patients (Boulain et al, Br J Anaesth 2016 117 :341-9).

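### The pain-day rate ratio takes the whole ICU stay as exposure although pain is rated only on awake, capable days, so it is distorted if the rated share of ICU days differs between arms

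*SAP*

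**What the plan says.** **SAP, Safety outcomes and analyses.** Four 0-to-10 scales are to be collected daily. A pain day is defined thus: "Each day, a patient will be considered as experiencing pain and/or discomfort if at least one scale is ≥ 4". The analysis of the count is: "The numbers of days with pain and/or discomfort will be compared between the groups with the use of a quasi-Poisson regression model", and it is "expressed as rate ratios, with the duration of stay in the ICU as the offset". The proportion of patients with at least one such day is compared by chi-squared test, with no denominator stated. I found no rule for days without a rating. I also found no Day-28 limit for this outcome, although the other quasi-Poisson counts, listed under Secondary outcomes analysis, run to Day 28.

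**Protocol 2.3, Outcome measures.** Device-related pain and discomfort are rated "once a day as soon as the patients are awakened and capable of correctly evaluating their pain and discomfort". Appendix 1 repeats the condition: "In both groups, once the patient alert and capable, we will assess his/her pain and discomfort related to the BP measuring device in place".

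**Protocol 4.6, Schedule of procedures.** The daily columns fall under "Short-term follow up until D28 or discharge from ICU (whichever comes first").

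**Protocol 6.2.** The planned analysis was on the daily values: "daily maximum pain and associated 95%CI will be estimated using mixed linear models". The SAP's summary of changes says that the device ratings were binarised because zeros made up more than 78.4% of responses for each scale and visit, and that this was chosen during data analysis.

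**SAP, Secondary outcomes analysis.** Secondary outcomes are unadjusted for multiplicity and are to be read as exploratory.

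**The concern.** The numerator and the exposure of the rate do not cover the same days. A pain day can arise only on a day when the patient gives a rating. The offset counts every ICU day, including days under sedation or in coma and, as worded, ICU days after Day 28, when scheduled daily follow-up has ended. Each such day enters the model as exposure without pain, although nothing is known about pain on that day.

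If the arms differ in how much of the ICU stay is rated, that difference is multiplied into the rate ratio and would be read as a difference in how painful the cuff and the catheter are. It could create an apparent difference or hide a real one.

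**Working it through.** **1. Plan's own figures.** The documents give no assumed rate, ratio or rated share for this outcome, so there is no figure to reproduce. The arm size used below is 1010/2 = 505. It agrees with Protocol 6.1: with mortality 22.5% vs 25%, margin 5 points, one-sided 2.5% and 80% power, n per arm = (1.960 + 0.842)² × (0.225×0.775 + 0.25×0.75) / 0.075² ≈ 505.

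**2. What the model estimates.** The SAP names no covariates for this model. In a quasi-Poisson model with group only and log(ICU days) as offset, the fitted ratio is

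RR(ICU offset) = (pain days / ICU days, noninvasive) / (pain days / ICU days, invasive).

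Let *a* be rated days divided by ICU days in an arm. Pain days per ICU day = pain days per rated day × *a*. Hence

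RR(ICU offset) = RR(per rated day) × a(noninvasive) / a(invasive).

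**3. Size for assumed shares, true ratio 1.00.**

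| Rated share, noninvasive | Rated share, invasive | RR with ICU-day offset |
|---|---|---|
| 50% | 50% | 1.00 |
| 55% | 50% | 0.55/0.50 = 1.10 |
| 50% | 40% | 0.50/0.40 = 1.25 |
| 45% | 50% | 0.45/0.50 = 0.90 |

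For an invasive-arm share between 30% and 60%, a 5-point difference moves the ratio by about 8% (0.65/0.60 = 1.083) to 17% (0.35/0.30 = 1.167). A 10-point difference moves it by about 17% (0.70/0.60) to 33% (0.40/0.30).

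**4. Simulation check.** There were 505 patients per arm and 400 replicates. ICU stays were capped at 28 days, and pain probability was 15% per rated day with variation between patients. Mortality was 25% vs 22.5%, with dying patients rated on 0.3 times the survivors' share of days. All of these except arm size and mortality are assumptions. With an invasive share of 50% among survivors and a true ratio of 1.00, noninvasive shares of 55%, 60%, 45% and 40% gave 1.14, 1.23, 0.93 and 0.81 with the ICU-day offset. With the rated-day offset the result was 0.99 to 1.01 throughout.

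A true ratio of 0.80 with shares of 60% (noninvasive) vs 50% (invasive) gave 0.995 with the ICU-day offset and 0.81 with the rated-day offset.

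**5. Mortality alone.** Assume equal shares in survivors, equal stays, and dying patients rated on a fraction *f* of the survivors' share. The factor is (0.775 + 0.225*f*) / (0.75 + 0.25*f*). For *f* = 0.3 it is 0.8425/0.825 = 1.02; for *f* = 0.05 it is 0.786/0.7625 = 1.03. The simulated values were 1.02 and 1.04.

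**6. Could another instrument fill the unrated days?** The schedule's footnote reads "assess by visual or numeric scale for patients able to communicate and by Behavioural Pain Scale(66) otherwise". It is attached to pain during vascular puncture, in a 10% sample. It does not supply device ratings for patients who cannot self-report.

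**The case against.** **Equal shares are plausible.** Randomisation is stratified on centre, invasive ventilation and vasopressor dose, and general care is meant to be the same in both arms. If so, the factor is 1.00. This stands: a reader might infer that the ratio is biased, or biased in a known direction, and the documents support neither. But stratification balances the arms only at entry. The protocol itself treats duration of ventilation, ventilator-free days and new intubation as outcomes that may differ, and these bear on whether a patient can rate.

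**Pain days per ICU day may be a burden measure.** It keeps all randomised patients and matches the offset of the other counts, whereas being rated is a post-randomisation state. The last point stands and is the reason to keep the ICU-day version. It does not justify leaving the plan unchanged: the SAP does not define a burden measure, an unrated day is not a known pain-free day, and catheter insertions, cultures or transfusions can be counted on any ICU day while a self-rating cannot.

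**Survival.** A reader might infer that differential death distorts the ratio materially. A stay shortened by death already shortens the offset, and the protocol's assumed mortality rates move the ratio only to about 1.02 to 1.04.

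**The chi-squared test.** A reader might infer that it counts never-rated patients as pain-free. The SAP does not state the denominator, so this needs clarification; it is not a demonstrated error.

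**Absolute rates.** A reader might also infer that they will be understated. The SAP plans only rate ratios for this model, and equal dilution cancels in a ratio.

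**Conclusion.** The mismatch between rated days and ICU-day exposure is in the text, and the multiplication in step 2 follows from the model, taken as unadjusted. Whether it distorts the comparison depends on one quantity that the documents do not give: the rated share of ICU days in each arm. For invasive-arm shares between 30% and 60%, a 5-point difference shifts the ratio by about 8% to 17% and a 10-point difference by about 17% to 33%. With equal shares there is no shift. The likeliest routes are sedation and ventilation.

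The consequence is confined to one exploratory patient-reported outcome, which the documents do not rank above the other secondary outcomes. The primary analysis, the non-inferiority conclusion and the 1010 patients are unaffected.

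**What to change.** - Use log(number of days with at least one completed rating, up to Day 28) as the offset for the pain-day model.
- Keep the ICU-day offset, limited to Day 28, as a sensitivity analysis.
- Report by arm the number of patients ever rated, the number of rated days, and rated days as a share of ICU days. A reader can then compute the factor in step 2 directly.
- State the denominator of the proportion with at least one pain day. Give it among patients with at least one rated day, alongside the all-patient figure.

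The cost is a few lines of SAP text and one derived variable. The SAP's own report of the share of zero responses by scale and visit indicates that completed ratings can be identified in the data. The downside is that the rated-day analysis conditions on a post-randomisation state and loses never-rated patients, so both versions should be shown.
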